	Principal Investigator:	[name] [name].
	Primary Contact Name/Contact Info:	[name] MD [contact] [name] MD
	Date Revised:	7/23/2017
	Study Number:	IF# 2089572, GCO#17-04301

Prospective triple blinded randomized control trial in patients undergoing foot and ankle surgeries. The research study will take place at Mount Sinai West hospital. The site PI is [name], MPH.

4)Resources Available to Conduct the Human Research

For n=200, the feasibility of recruitment is manageable. Recruitment will be done through a coordination of the operating schedule and the surgeon’s office. Patients presenting for preoperative visits at the surgeon’s office or the preoperative joint clinic will be approached. The surgeon will also provide study information (protocol, consent, general information) to patients in the surgeon’s office. After confirmation on the operating schedule, patients will be provided detailed instructions the day before surgery and the final consent will be obtained at the surgeon’s office or joint clinic for patients at Mount Sinai West hospital. On the day of the surgery, the subject will meet the research team in the holding area. The team will finalize participation and ask the subject about the signed consent forms and answer any additional questions. The staff members on this protocol are all employees of Mount Sinai and will either be a resident or attending physicians that are included on the IRB protocol. There are three primary members of the research personnel:

a)[name], MPH – Roles for [name] in this study include serving as primary investigator responsible for study design and planning, data collection, subject recruitment, manuscript writing and preparation, data analysis, safety monitoring, and responding to adverse events and/or complications. He is certified in PPHS/IRB protocols, all Citi/IRB required training in human subject protection, and has prior clinical research experience. He is also a board certified anesthesiologist and assistant professor of anesthesiology with the Icahn School of Medicine and the Mount Sinai Health System.

b) [name] MD – Roles for [name] include serving as primary research coordinator involved in data collection, subject recruitment, manuscript writing and preparation, data analysis, safety monitoring, and responding to adverse events

	Protocol Name:	EFFICACY OF TRANEXAMIC ACID IN FOOT AND ANKLE SURGERIES - A RANDOMISED CONTROLLED TRIAL
	Principal Investigator:	[name] [name].

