	Primary Contact Name/Contact Info:	[name] MD [contact] [name] MD
	Date Revised:	7/23/2017
	Study Number:	IF# 2089572, GCO#17-04301

entering in [SECURE] in the e-mail subject line. Once recruited blinding assessments will be done by the study team.

Patients will be assigned randomly using a computer- generated table of numbers to either TXA group (Tranexamic acid group) or placebo (saline group). Patients assigned to TXA group will receive 10mg/kg IV TXA in a 100cc normal saline bag at the time of induction and a second dose prior to skin closure. Patients in the placebo group will receive 100cc normal saline IV at the time of induction and a second dose prior to skin closure. Otherwise, the patient, surgeon, and anesthesiologist in the case will be blinded.

a) Recruitment methods: Patients will be recruited and consented at the surgeons office or pre-operative testing/Joint clinic.

b) Inclusion and Exclusion Criteria

Inclusion criteria: ASA (American Society of Anesthesiology) class I-IV, age 18-75.

Exclusion criteria: ASA class V, patient refusal, patients with known coagulopathy disorder, renal insufficiency, hepatic dysfunction, serious cardiac disease, patients receiving antiplatelet and/or anticoagulant drugs, or an allergy to TXA or will be excluded.

c)Number of Subjects

We intend to recruit 200 patients.

Based on a confidence level of 99% with a Z score of 2.58, standard deviation of .5 and a confidence interval of 10% our sample size should be 166. For ease of statistical calculations we rounded up to 200 patients. Literature search reveals only one previous study where TXA has been used in calcaneal fractures. Xie et al concluded in a study with 90 patients that TXA reduces post operative blood loss. We intend to use a higher sample size to see any statistical significance.

	Protocol Name:	EFFICACY OF TRANEXAMIC ACID IN FOOT AND ANKLE SURGERIES - A RANDOMISED CONTROLLED TRIAL
	Principal Investigator:	[name] [name].
	Primary Contact Name/Contact Info:	[name] MD [contact] [name] MD
	Date Revised:	7/23/2017
	Study Number:	IF# 2089572, GCO#17-04301

$$Z^2 * (p) * (1-p)$$

$$SS = \frac{\quad}{c^2}$$

Where:

Z = Z value (2.58 for 99% confidence level)
p = percentage picking a choice, expressed as decimal (.5 used for sample size needed)
c = confidence interval, expressed as decimal (e.g., .01= ±1)

Sample size= [(2.58²)(.5)(.5)]/(.1²)=166 subjects
For effect size, we expect a Cos d medium effect of 0.5.

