Intergroup comparisons will be performed using the Mann-Whitney U test. Qualitative data will be compared using the chi-square test or Fisher’s exact test. Only p < .05 will be considered statistically significant.

d)Study Timelines

2018-2019 and subsequent data analysis. The subject’s participation will be from time of enrollment in the pre-operative period until first postoperative day. The first follow up visit at the surgeons office will be included as well. Estimated date of enrollment completion will be when 200 eligible subjects are enrolled in final data analysis. Estimate date for study completion will be June 2018.

	Protocol Name:	EFFICACY OF TRANEXAMIC ACID IN FOOT AND ANKLE SURGERIES - A RANDOMISED CONTROLLED TRIAL
	Principal Investigator:	[name] [name].
	Primary Contact Name/Contact Info:	[name] MD [contact] [name] MD
	Date Revised:	7/23/2017
	Study Number:	IF# 2089572, GCO#17-04301

e)Endpoints

Conclusion of data analysis and evaluation of significance of findings, as measured by primary and secondary outcomes listed under Objectives (item #1) for purposes of quality improvement.

f)Procedures Involved in the Human Research

Prospective randomized controlled trial and data analysis only. TXA group and placebo group. Intraoperative care of the patient will be provided by an anesthesia team member who is a part of the Mount Sinai System. The anesthesia provider will not be aware of the randomization of the patient. Standard post-operative orders will be written for patients during their time in the PACU.

g)Specimen Banking

N/A

h)Data Management and Confidentiality

Data collected in excel file to be de-identified after initial collection. Excel file be subsequently encrypted and shared only between the above listed investigators via secure Mt. Sinai (chpnet) electronic mail.

The information included in the data will be medical record number, age, gender, ASA class, type of surgery, duration of surgery, the amount of intra operative and post operative blood loss during the first 24 hours in patients will be collected. Wound complications (eg dehiscence, hematoma, necrosis and infection), wound healing time and length of stay will be evaluated. Post operative complete blood count will be recorded. The first follow up at surgeon’s office will be the other data collected.

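### Section 5c sizes a two-arm comparison with a one-sample precision formula, so its 166 patients and ±10 points do not describe the TXA-placebo difference

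*Combined protocol and SAP*

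**What the plan says.** Section 5c (Number of Subjects) opens its justification with "Based on a confidence level of 99% with a Z score of 2.58, standard deviation of .5 and a confidence interval of 10" per cent, and reaches 166 from Z²·p·(1−p)/c². The key to the formula defines "p = percentage picking a choice, expressed as decimal (.5 used for sample size needed"). The step from 166 to the planned number is explained by "For ease of statistical calculations we rounded up to 200 patients". The section then cites one earlier study of 90 patients with calcaneal fractures, which reported on postoperative blood loss, and adds "We intend to use a higher sample size to see any statistical significance". After the calculation comes one more line: "For effect size, we expect a Cos d medium effect of 0.5".

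The design is comparative. Section 5 (Study Design) says "Patients will be assigned randomly using a computer- generated table of numbers to either TXA group (Tranexamic acid group) or placebo (saline group"). The analysis paragraph at the end of 5c says "Intergroup comparisons will be performed using the Mann-Whitney U test", assigns qualitative data to the chi-square or Fisher's exact test, and sets significance at p < .05.

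Section 1 (Objectives) names the incidence of wound complications first under the primary outcome. Wound healing time and length of stay are in the same paragraph. Blood loss over the first 24 hours is secondary.

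Section 4 says of the chosen number only that "For n=200, the feasibility of recruitment is manageable".

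**The concern.** The formula answers a survey question: how many people are needed to estimate one percentage to within ±10 points. The trial asks whether two randomised groups differ. Sizing that question needs an expected rate or spread in the placebo arm, a difference worth detecting, a significance level and a power. Section 5c supplies none of these in its calculation. The effect size of 0.5 could have been one of them, but it is stated after the result, is attached to no outcome, and is not a natural scale for an incidence.

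A reader of 5c may therefore believe that the TXA-placebo comparison carries 99% confidence and ±10 points. It does not. For the incidence of wound complications, the plan also makes no valid advance statement of what the trial could detect. A non-significant result could then be over-read as absence of effect, although the confidence interval actually observed would still be informative.

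**Working it through.** **Inputs from the protocol.** Z = 2.58, p = .5, c = .1, the result 166, the planned 200, two arms, p < .05, and chi-square, Fisher or Mann-Whitney tests (sections 5 and 5c).

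**Assumptions, because the supplied text does not state them.** 1:1 allocation, two-sided testing, no loss, and placebo complication rates of 5% to 40%.

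**1. The plan's own figure.** 2.58² × .5 × .5 / .1² = 6.6564 × .25 / .01 = 166.41. The 166 reproduces.

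**2. Precision of the comparison at the same p.** The half-width for a difference between two proportions is Z × √(2p(1−p)/n per arm). At p = .5, 2p(1−p) = .5.
- 83 per arm, 99%: 2.58 × √(.5/83) = .200, or ±20.0 points.
- 100 per arm, 99%: 2.58 × √(.5/100) = .182, or ±18.2 points.
- 100 per arm, 95%: 1.96 × √(.5/100) = .139, or ±13.9 points.

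With 83 per arm the half-width is twice the stated ±10: each arm holds half the patients, and the variances of two arms add.

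**3. What 100 per arm offers for the incidence.** The effect illustrated is a halving of the placebo rate. Power comes from full enumeration of two Binomial(100) arms at two-sided 5%, with the uncorrected chi-square test and with Fisher's exact test. The 95% half-width is 1.96 × √((p₁q₁ + p₂q₂)/100), where q = 1 − p.

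| Assumed placebo rate | TXA rate | p₁q₁ + p₂q₂ | Power, chi-square | Power, Fisher | 95% half-width |
|---|---|---|---|---|---|
| 5% | 2.5% | .0719 | 13% | 7% | ±5.3 |
| 10% | 5% | .1375 | 27% | 19% | ±7.3 |
| 20% | 10% | .2500 | 52% | 44% | ±9.8 |
| 30% | 15% | .3375 | 73% | 67% | ±11.4 |
| 40% | 20% | .4000 | 88% | 84% | ±12.4 |

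From an assumed 5%, even zero events on TXA gives only 74% power (chi-square) or 38% (Fisher), so no lower TXA rate reaches 80%. A halving reaches 80% power from a placebo rate of about 34% (chi-square) or 37% (Fisher).

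**4. If the 0.5 is Cohen's d for a continuous outcome.** With 100 per arm the expected test statistic is .5 × √(100/2) = 3.54. The two-sample t-test then has 94% power. Mann-Whitney with roughly normal data has a relative efficiency of .955, equivalent to 95.5 per arm, and 93% power. Neither calculation appears in the protocol.

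**The case against.** *200 may be enough.* This stands. A reader might infer from the wrong formula that the trial is too small, but the documents do not support that. They give no placebo complication rate and no target difference. Under the assumed rates, power for a halving runs from poor to good. For a standardised effect of 0.5 on a continuous outcome it exceeds 90%.

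*The 0.5 already justifies 200.* It could be relevant to wound healing time or length of stay, which sit in the primary-outcome paragraph, or to blood loss. It would therefore go too far to say that no outcome in the trial could be adequately powered. But the protocol never makes the link, and the 0.5 cannot serve as the basis for the incidence.

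*The 99% level contradicts testing at 5%.* A reader might take this as a second error. It is a minor point: a confidence level for precision and a significance level for a test are different quantities, and a stricter level for sizing is conservative.

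*±10 points is sometimes achieved.* True for rare events. For a halving with 100 per arm at 99%, the half-width is 10 points when 1.5p − 1.25p² = (.1/2.58)² × 100 = .1502, that is, at an assumed placebo rate of about 11%. Above that and up to the 40% considered here, it is wider. Section 5c does not argue from a low rate; it uses p = .5.

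*The placebo rates are invented.* They are assumptions and must be labelled so. The main finding in steps 1 and 2 does not use them. The chi-square figures at the lowest rate are also optimistic if Fisher's test is the one applied there; the protocol gives no rule for choosing.

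*Feasibility is the real basis.* Section 4 does not say so. It says that recruiting a number already chosen is manageable.

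**Conclusion.** The point holds as an error of justification. The formula in 5c does not size the comparison the trial will test, and its ±10 points becomes ±20.0 (83 per arm) or ±18.2 (100 per arm) for the TXA-placebo difference at the same p = .5 and 99% level. The effect size of 0.5 is unused and tied to no outcome. Being larger than a 90-patient study of blood loss is not a power calculation either.

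This should be fixed, but it changes wording only: the arithmetic is correct, and 200 is not shown to be inadequate. The half-widths rest on equal allocation; the power figures rest in addition on two-sided testing, no loss and assumed placebo rates. Section 5c is complete in the supplied text; a part between sections 5h and 5j was not available and could not be checked.

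**What to change.** Keep 200, the tests and the significance level. Then:

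1. Delete the survey formula and the 99%/±10% statement from 5c.
2. Have the investigators state the real basis for 200. Feasibility may be given only if they confirm it.
3. Add a short statement of what 200 delivers, for example:

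> With 100 per arm (1:1 allocation and no loss assumed) and two-sided p < .05, power to detect a halving of the wound-complication incidence from assumed placebo rates of 10%, 20%, 30% and 40% is about 27%, 52%, 73% and 88% by chi-square (19%, 44%, 67% and 84% by Fisher's exact test). The 95% half-widths for the difference are about ±7.3, ±9.8, ±11.4 and ±12.4 points. From an assumed 5%, power for a halving is 7% (Fisher) to 13% (chi-square), and no lower TXA rate reaches 80%.

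The placebo rates must stay labelled as assumptions, or be replaced by one rate that the investigators can justify.

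4. Have the investigators confirm what the 0.5 measures and which outcome it concerns. Only if it is Cohen's d for a continuous outcome, add that 100 per arm gives about 93% power by Mann-Whitney with roughly normal data (94% by t-test). Do not present it as the basis for the incidence.

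The cost is protocol wording, and a stated precision less favourable than the present ±10 points suggests.

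### Type of surgery is collected but not used in the blood-loss comparison: a cheap possible gain in efficiency, with no effect on validity and almost none on the primary outcome

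*Combined protocol and SAP*

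**What the plan says.** Section 3 describes the trial as "Prospective triple blinded randomized control trial in patients undergoing foot and ankle surgeries". Section 5b sets the entry rule: "Inclusion criteria: ASA (American Society of Anesthesiology) class I-IV, age 18-75". The exclusions that follow are medical, and none limits the kind of operation.

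Section 5 describes allocation: "Patients will be assigned randomly using a computer- generated table of numbers to either TXA group" or placebo. It mentions no strata.

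The last paragraph of Section 5c gives the whole analysis plan: "Intergroup comparisons will be performed using the Mann-Whitney U test. Qualitative data will be compared using the chi-square test", with Fisher's exact test as the alternative, and "Only p < .05 will be considered statistically significant". It names no covariate, stratified test or adjusted model.

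Section 5h lists the data to be held, beginning with "medical record number, age, gender, ASA class, type of surgery, duration of surgery". Section 4 shows that the operation is known before the day of surgery: "After confirmation on the operating schedule, patients will be provided detailed instructions the day before surgery".

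Section 1 makes wound complications the primary outcome and blood loss over the first 24 hours a secondary one. However, the research question in Section 1 and the aim in Section 2 are both about postoperative bleeding. The only effect size is in Section 5c: "For effect size, we expect a Cos d medium effect of 0.5". It is tied to no outcome and does not enter the sample-size formula.

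**The concern.** Foot and ankle operations may differ in how much they bleed. If they do, an unadjusted comparison leaves those differences in the error term and the treatment effect is estimated less precisely than the data allow. The variable that would remove them is already on the data sheet and can be fixed before treatment.

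What is at stake is power and interval width for blood loss. The type I error rate is not at stake.

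**Working it through.** **The plan's own figure.** Section 5c uses Z²p(1−p)/c². With Z = 2.58, p = 0.5 and c = 0.10 this is 6.6564 × 0.25 / 0.01 = 166.4, which matches the stated 166, later raised to 200. This is a precision formula for one proportion. It gives no power for a two-group comparison, so a baseline has to be computed.

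**Inputs.** From the documents: 200 patients, p < .05, d = 0.5. Assumed, because the documents are silent: 100 per arm, a two-sided test, d = 0.3 as a smaller effect, R² from 0 to 0.5, and class sizes and risks as shown.

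**Normal-theory approximation for blood loss.** Removing a share R² of the variance raises the standardised effect to d/√(1−R²). Power is then about Φ(d/√(1−R²) × √(100/2) − 1.96), and the effective number per arm is 100/(1−R²).

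| R² | Effective n per arm | Power, d = 0.3 | Power, d = 0.5 |
|---|---|---|---|
| 0 | 100 | 56.4% | 94.2% |
| 0.1 | 111 | 60.9% | 96.1% |
| 0.3 | 143 | 71.8% | 98.8% |
| 0.5 | 200 | 85.1% | 99.9% |

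**Simulation of the rank tests.** Planned Mann-Whitney against van Elteren; three classes (30/40/30%), unstratified allocation, normal residuals, the same effect in every class, 6,000 runs:

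| R² | d = 0.3 | d = 0.5 |
|---|---|---|
| 0 | 54.3% → 53.4% | 92.5% → 92.2% |
| 0.1 | 54.6% → 57.7% | 93.3% → 94.9% |
| 0.2 | 53.7% → 62.7% | 92.7% → 97.1% |
| 0.5 | 51.9% → 82.6% | 92.2% → 99.8% |

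Two classes (70/30%) give much the same: at d = 0.3, 54.2% → 58.6% for R² = 0.1 and 54.3% → 81.9% for R² = 0.5. With no treatment effect, both tests reject in about 5% of runs (4.8 to 5.7% for Mann-Whitney, 4.9 to 5.5% for van Elteren). With skewed or heavy-tailed residuals the gain is about 1.5 to 4 points at d = 0.5 (from 96 to 98%) and 7 to 31 points at d = 0.3 (from 60 to 67%).

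**Number of classes.** With four classes and R² = 0, power at d = 0.3 fell from 54.2% to 52.6%, a loss of 1.6 points. With two or three classes the loss was at most about 1 point. Hence the advice to use few classes.

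**If the effect differs by class.** Suppose the low-bleeding class has a quarter of the effect of the high-bleeding class. Then at R² of 0.1 to 0.2 the change from stratifying is about −0.7 to +1.7 points at an average d = 0.5, and +1 to +6 points at d = 0.3. Suppose instead that the whole effect lies in a 30% class. Van Elteren then loses about 1 to 5 points at d = 0.3 and about 9 at d = 0.5. The last case is extreme: an average of 0.5 SD means 0.5/0.30 = 1.67 SD within that class.

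**Wound complications.** Chi-square against Cochran-Mantel-Haenszel (CMH), 10,000 runs each:

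| Control risks by class | R² | Odds ratio | Chi-square → CMH |
|---|---|---|---|
| .10/.30 (75/25%) | .059 | 0.5 | 32.3% → 32.9% |
| .10/.40 (70/30%) | .123 | 0.4 | 51.4% → 54.3% |
| .10/.40 (70/30%) | .123 | 0.25 | 80.8% → 83.2% |
| .05/.12/.25 (30/40/30%) | .052 | 0.4 | 44.3% → 44.3% |
| .15/.15 | 0 | 0.4 | 49.2% → 48.4% |

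The gain is about 0 to 3 points, and about 1 point is lost when the classes do not differ. Exact CMH gains about 4 to 6 points over Fisher, but about 4 of those appear at R² = 0 as well, because exact CMH is less conservative. They do not come from knowing the type of surgery.

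**The case against.** The strongest reply is that nothing here is broken. The planned tests hold their error rate, the primary outcome hardly benefits, and at the protocol's d = 0.5 the rank test already has about 93% power. The largest gains need both R² = 0.5 and an effect that the documents do not state. The gains also assume one effect for every class; where that fails they can vanish or reverse. All of this stands. It fixes the severity as low and means that the change cannot be called free.

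Two practical replies also stand. Section 5h does not say whether the recorded type of surgery is the scheduled or the performed one, and only the scheduled one is sure to be fixed before treatment. And the van Elteren test alone gives a p-value, so a gain in precision reaches the reader only if an adjusted estimate with an interval is reported.

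What does not follow is that the point should be dropped. Bleeding is what the research question asks about, d = 0.5 is not tied to blood loss, and at d = 0.3 the unadjusted test has only about 54% power.

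A reader might infer more: that open entry without stratification biases the comparison through chance case-mix imbalance. With 100 per arm, a procedure type seen in 20% of patients can differ between arms by 1.96 × √(2 × 0.2 × 0.8/100) = 11 percentage points by chance. But randomisation covers this: the unadjusted tests already allow for it, and their simulated error rate stays near 5%. It is the same loss of precision and must not be counted twice.

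**Conclusion.** The point holds as a cheap improvement of low severity. A recorded variable that can be defined before treatment is used neither in the allocation as described nor in any planned test.

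The likely benefit is confined to blood loss: about 2 to 8 power points at d = 0.5 and about 3 to 30 at d = 0.3. This rests on R² of 0.1 to 0.5, 100 per arm, two-sided .05 and a common effect. None of the R² values comes from the documents. About 1 point is lost if type of surgery predicts nothing. The change is about −1 to +6 points at R² of 0.1 to 0.2 if the effect is much larger in high-bleeding procedures, and several points can be lost if it sits in a small class.

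Two stronger readings fail. The documents do not support calling the planned analysis invalid. Nor do they support expecting stratification to repair power for wound complications, where it adds about 0 to 3 points at best.

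**What to change.** Before unblinding, write down two or at most three broad classes of the scheduled operation. Analyse blood loss by the van Elteren test stratified by class. Report a stratified or class-adjusted treatment difference with a 95% CI, with the estimator named in advance. Keep the unadjusted Mann-Whitney test as a sensitivity analysis. Leave chi-square or Fisher's exact test in place for wound complications.

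Do not adjust for duration of surgery: it accrues after the first dose and Section 1 lists it among the outcomes.

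Stratify the allocation list only if enrolment has not begun, and then stratify the tests by the same classes. In simulation with a stratified list, plain Mann-Whitney rejected a true null in only 3.9%, 2.6% and 0.4% of runs at R² of 0.1, 0.2 and 0.5. It becomes conservative and wastes the stratification.

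The cost is one definition of classes, a little extra analysis, and making sure that the data sheet records the scheduled procedure, which may need an added entry. The power risk is the one given in the verdict.
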